7.10.4.3 Proportions of LARS Severity Group at Baseline and Post-baseline Assessment

Based on the LARS total score of LARS, a patient can be classified into one of the following 4 groups: 0 to 20 (no LARS), 21 to 29 (minor LARS), and 30 to 42 (major LARS). Proportions of patients in each of these four groups and associated 95% confidence interval will be calculated at baseline and each time of post-baseline assessments (**Table 52**).

8. Appendices

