1.2 Secondary Objectives

1. To describe the 3-year Locoregional Relapse Rate (LRR) in patients treated with organ preservation.
2. To describe the 3-year Distant Relapse Rate (DRR) in patients treated with organ preservation.
3. To describe the 3-year Disease Free Survival (DFS) rate in patients treated with organ preservation.
4. To evaluate the rate of post-operative complications following neoadjuvant FOLFOX/CAPOX and tumour excision/surgery.
5. To evaluate nature, severity and frequency of acute and long term toxicities in all patients.
6. To evaluate Quality of Life (QoL) in all patients.
7. To evaluate the cost-effectiveness of the neo-adjuvant chemotherapy approach vs. the current standard approach.

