2.0 BACKGROUND INFORMATION AND RATIONALE

Colorectal cancer is the second most common cause of cancer death in North America, with rectal neoplasms accounting for one third of incident cases. The introduction of provincial colorectal cancer screening programs has led to earlier diagnosis and 35-40% of rectal tumours present with localized disease [Jemal 2008]. Current standard therapy for T1-3 tumours includes radical surgery with Total Mesorectal Excision (TME), and preoperative chemoradiation for patients with T3 tumours or N1 tumours. Locoregional relapse rates with modern adjuvant therapy are generally 5% [Hong 2014; O'Connell 2014; Rodel 2014]. Even with laparoscopic surgery, surgical complication rates are significant and temporary diverting ostomies are associated with significant morbidity and the requirement for second surgery for reversal [Alberts 2012]. In patients treated with radical resection, ongoing issues with bowel function, incontinence, sexual function and depression persist. These are significantly worse in patients treated with neoadjuvant or adjuvant radiotherapy [Wiltink 2014].

Patients with low tumours, < 5 cm from the anal verge, commonly require permanent colostomies and the rates of non-sphincter sparing surgery in phase III trials of stage II/III rectal cancer is consistently 25% [Gerard 2012; Allegra 2014]. Loss of the rectum and a permanent colostomy has dramatic effects on quality of life, sexual/urinary and social function and at high economic cost.

Multiple single arm and randomized phase II studies have explored the use of pelvic chemoradiation (chemoXRT) followed by Transanal Endoscopic Microsurgery (TEMS) or Transanal Minimally Invasive Surgery (TAMIS) as a means to increase rectal organ preservation [Lezoche 2012]. However, even with minimally invasive surgery like TEMS/TAMIS, neoadjuvant radiation significantly increases wound-healing complications [Marks 2009] and adversely affects sphincter [Hupkens 2015] and sexual function. Furthermore, patients who develop recurrence with this strategy are difficult to salvage as radiotherapy is no longer an option. Conversely, there is virtually no prospective experience of neoadjuvant FOLFOX/CAPOX chemotherapy and excision/surgery for early rectal tumours.

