LARS and the Fecal Incontinence Quality of Life Instrument		X		X			6, 12, 24 and 36		
Health Economics									
EQ-5D-5L		X	X ¹⁹	X		X	6, 12, 24 and 36		
Phone Contact									
Survival information								X	X
1. Timing for visits after excision are scheduled from last tumour excision date: a. For patients having TME as first protocol excision: from TME date b. For patients having TEMS/TAMIS as first protocol excision: from TEMS/TAMIS date c. For patients having TEMS/TAMIS as first protocol excision and then having a TME: from TME date 2. See protocol section 8 for definitions. 3. Phone contacts or visits after first disease relapse are required every 6 months from date of relapse. 4. Tests may be done on the date of treatment or, if not possible, the previous working day before treatment day. If treatment is to begin on a Monday, may be done on the previous Friday (maximum 72 hours prior to treatment). 5. Please also see protocol Section 12.0 and details for collection, processing, storing, and shipping these samples provided in the CO.28 Correlative Studies Manual. 6. Whole blood (that is not for ctDNA testing) will only be collected prior to enrollment. 7. Not required for patients that had a TME. 8. To be obtained within 28 days as close to the time of relapse as possible. Blood for correlatives done within 28 days PRIOR to date of relapse does not need to be repeated. 9. For CT pelvis and chest, a CT scan with contrast is preferred but not mandated. Patients with contrast allergies may undergo chest X-ray and /or Chest MRI. 10. Contrast is REQUIRED for the CT scan of the abdomen. Patients with contrast allergies may undergo liver ultrasound and /or MRI. 11. Rectal exam and proctoscopy are ideally to be performed by the primary surgeon. Proctoscopy should be performed ≤ 90 days prior to enrollment. Ideally, the surgeon should perform pre and post induction treatment proctoscopies. A gastroenterologist may perform proctoscopy in lieu of the surgeon, but then must also perform the follow-up exam. Proctoscopy may be accomplished using rigid proctoscopy or as part of a flexible sigmoidoscopy or colonoscopy. 12. For patients that had a TME it is only required at month 36. 13. If a rectal tumour tissue biopsy was performed within 90 days prior to enrollment, a repeat biopsy is not necessary. It is recommended that surgeons take a biopsy of the tumour during sigmoidoscopy/colonoscopy to ensure tissue availability and adequate pathology report confirming invasive well-moderately differentiated rectal adenocarcinoma and no evidence of pathologic high risk factors. 14. It is strongly encouraged that suspicious or unequivocal evidence of first local relapse be confirmed definitively by either biopsy (preferred) or by repeat/confirmatory imaging. Where imaging evidence of first local relapse is, in the opinion of the investigator and radiologist, absolutely unequivocal and not requiring subsequent confirmation by either biopsy or follow-up imaging, this must be clearly indicated in supporting documentation. 15. Urine pregnancy test in women of childbearing potential and if a false-positive is suspected this may include an ultrasound to rule-out pregnancy. 16. To be completed daily for patients receiving Capecitabine. 17. Adverse Events to be evaluated using the NCI Common Terminology Criteria for Adverse Events (CTCAE v5.0) (see Appendix III). 18. Only protocol chemotherapy or surgery related adverse events have to be reported after the 30 days post-excision visit. 19. After 3 cycles of FOLFOX or after 2 cycles of CAPOX.									

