25. Have you had difficulty remembering things?	1	2	3	4
26. Has your physical condition or medical treatment interfered with your family life?	1	2	3	4
27. Has your physical condition or medical treatment interfered with your social activities?	1	2	3	4
28. Has your physical condition or medical treatment caused you financial difficulties?	1	2	3	4

For the following questions please circle the number between 1 and 7 that best applies to you.

29. How would you rate your overall health during the past week?	1 Very Poor	2	3	4	5	6	7 Excellent
30. How would you rate your overall quality of life during the past week?	1 Very Poor	2	3	4	5	6	7 Excellent

Patients sometimes report that they have the following symptoms. Please indicate the extent to which you have experienced these symptoms during the past week.

During the past week:	Not At All	A Little	Quite a Bit	Very Much
31. Did you urinate frequently during the day?	1	2	3	4
32. Did you urinate frequently during the night?	1	2	3	4
33. Have you had any unintentional release (leakage) of urine?	1	2	3	4
34. Did you have pain when you urinated?	1	2	3	4
35. Did you have abdominal pain?	1	2	3	4
36. Did you have pain in your buttocks/anal area/rectum?	1	2	3	4
37. Did you have a bloated feeling in your abdomen?	1	2	3	4
38. Have you had blood in your stools?	1	2	3	4
39. Have you had mucus in your stools?	1	2	3	4
40. Did you have a dry mouth?	1	2	3	4
41. Have you lost hair as a result of your treatment?	1	2	3	4
42. Have you had problems with your sense of taste?	1	2	3	4
43. Were you worried about your health in the future?	1	2	3	4
44. Have you worried about your weight?	1	2	3	4
45. Have you felt physically less attractive as a result of your disease or treatment?	1	2	3	4
46. Have you been feeling less feminine/masculine as a result of your disease or treatment?	1	2	3	4
47. Have you been dissatisfied with your body?	1	2	3	4

48. Do you have a stoma bag (colostomy/ileostomy)?
(please circle the correct answer)

Yes

No

During the past week:

Not
At All A
Little Quite
a Bit Very
Much

Answer these questions ONLY IF YOU HAVE A STOMA BAG, if not please continue below:

49. Have you had unintentional release of gas/flatulence from your stoma bag?

1 2 3 4

50. Have you had leakage of stools from your stoma bag?

1 2 3 4

51. Have you had sore skin around your stoma?

1 2 3 4

52. Did frequent bag changes occur during the day?

1 2 3 4

53. Did frequent bag changes occur during the night?

1 2 3 4

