54. Did you feel embarrassed because of your stoma?

1 2 3 4

55. Did you have problems caring for your stoma?

1 2 3 4

Answer these questions ONLY IF YOU DO NOT HAVE A STOMA BAG:

49. Have you had unintentional release of gas/flatulence from your back passage?

1 2 3 4

50. Have you had leakage of stools from your back passage?

1 2 3 4

51. Have you had sore skin around your anal area?

1 2 3 4

52. Did frequent bowel movements occur during the day?

1 2 3 4

53. Did frequent bowel movements occur during the night?

1 2 3 4

54. Did you feel embarrassed because of your bowel movement?

1 2 3 4

During the past 4 weeks:

Not
At All A
Little Quite
a Bit Very
Much

For MEN only:

56. To what extent were you interested in sex? 1 2 3 4

57. Did you have difficulty getting or maintaining an
erection? 1 2 3 4

For WOMEN only:

58. To what extent were you interested in sex? 1 2 3 4

59. Did you have pain or discomfort during intercourse? 1 2 3 4

Fecal Incontinence Quality of Life Instrument

Q 1: In general, would you say your health is:

- 1 Excellent
- 2 Very Good
- 3 Good
- 4 Fair
- 5 Poor

Q 2: For each of the items, please indicate how much of the time the issue is a concern for you due to accidental bowel leakage.

Q2. Due to accidental bowel leakage:	Most of the Time	Some of The Time	A Little of the Time	None of the Time
	1	2	3	4
a. I am afraid to go out.				
b. I avoid visiting friends.	1	2	3	4
c. I avoid staying overnight away from home.	1	2	3	4
d. It is difficult for me to get out and do things like going to a movie or to church.	1	2	3	4
e. I cut down on how much I eat before I go out.	1	2	3	4
f. Whenever I am away from home, I try to stay near a restroom as much as possible.	1	2	3	4
g. It is important to plan my schedule (daily activities) around my bowel pattern.	1	2	3	4
h. I avoid traveling.	1	2	3	4
i. I worry about not being able to get to the toilet in time.	1	2	3	4
j. I feel I have no control over my bowels.	1	2	3	4
k. I can't hold my bowel movement long enough to get to the bathroom.	1	2	3	4
l. I leak stool without even knowing it.	1	2	3	4
m. I try to prevent bowel accidents by staying very near a bathroom.	1	2	3	4

Q 3: Due to accidental bowel leakage, indicate the extent to which you AGREE or DISAGREE with each of the following items.

Q3. Due to accidental bowel leakage:	Strongly Agree	Somewhat Agree	Somewhat Disagree	Strongly Disagree
a. I feel ashamed.	1	2	3	4
b. I can not do many of things I want to do.	1	2	3	4

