7.10.1.3 Low Anterior Resection Syndrome (LARS) Score

Low Anterior Resection Syndrome (LARS) Score is a scoring system for bowel dysfunction after low anterior resection (LAR) for rectal cancer. It consists of 5 questions and the answers to them are assigned a score based on the following algorithm:

Question 1: Do you ever have occasions when you cannot control your flatus (wind)?

- No, never 0
- Yes, less than once per week 4
- Yes, at least once per week 7

Question 2: Do you ever have any accidental leakage of liquid stool?

- No, never 0
- Yes, less than once per week 3
- Yes, at least once per week 3

Question 3: How often do you open your bowels?

- More than 7 times per day (24 hours) 4
- 4-7 times per day (24 hours) 2
- 1-3 times per day (24 hours) 0
- Less than once per day (24 hours) 5

Question 4: Do you ever have to open your bowels again within one hour of the last bowel opening?

- No, never 0
- Yes, less than once per week 9
- Yes, at least once per week 11

Question 5: Do you ever have such a strong urge to open your bowels that you have to rush to the toilet?

- No, never 0
- Yes, less than once per week 11
- Yes, at least once per week 16

LARS total score is defined as the sum of scores to these 5 questions.

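### LARS is summed and banded without regard to stoma status, so scores with no clear meaning enter the pooled LARS tables and probably overstate the 'No LARS' proportion

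*SAP*

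**What the plan says.** - Protocol 1.2 sets the aim "To evaluate Quality of Life (QoL) in all patients". In the Section 5.0 flowsheet, the row "LARS and the Fecal Incontinence Quality of Life Instrument" is due before enrollment, pre-excision and at months 6, 12, 24 and 36. The questionnaire cover page in Appendix V counts those months from the TME date for patients who proceed to TME.
- The same flowsheet exempts TME patients from other assessments. Footnote 7, on blood samples and pelvic MRI, reads "Not required for patients that had a TME", and footnote 12 reduces their endoscopy to month 36. Neither footnote is attached to the LARS/FIQL row.
- The LARS form in Appendix V has five questions, with no stoma question and no not-applicable answer. CR29, in the same booklet, asks about a stoma bag at item 48 and then branches. One block is headed "Answer these questions ONLY IF YOU DO NOT HAVE A STOMA BAG".
- SAP 7.10.1.3 states: "LARS total score is defined as the sum of scores to these 5 questions". The rule at the end of SAP 7.10.1.4 applies to all instruments: mean imputation if at least half the items of a scale are present, otherwise missing.
- SAP 7.10.4.1 reports LARS means and change scores (Tables 49 and 50). SAP 7.10.4.3 bands the total as 0-20, 21-29 and 30-42: "Proportions of patients in each of these four groups and associated 95% confidence interval will be calculated". The text announces four groups but lists three, and Table 52 has three.
- The analysis set (SAP 6 and 7.10.2) is anyone with at least one questionnaire. Protocol 13.6 describes only the two EORTC questionnaires, so it adds no rule for LARS.

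**The concern.** The LARS items concern control of wind and liquid stool, bowel frequency, returning within an hour, and urgency. SAP 7.10.1.3 itself presents the score as a measure for use after low anterior resection. While stool is diverted through a stoma, these questions have no clear meaning, yet the plan turns any sufficiently complete form into a score and a band. The most natural answer, that none of these things ever happens, earns the best band. A patient who has lost anorectal function would then count as having no bowel dysfunction.

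Stomas are foreseeable here. The Protocol Background describes permanent colostomies for low tumours and temporary diverting ostomies after radical surgery, and SAP 7.8.3.1 lists a diverting ostomy among reoperations. The Background also expects organ-sparing treatment to give better function than radical surgery with possible stoma formation, so the error would fall on a question of interest to the trial.

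**Working it through.** **1. The plan's own range.** The highest item scores in SAP 7.10.1.3 are 7, 3, 5, 11 and 16. Their sum is 42 and the minimum is 0, which matches the 0-42 span of the bands in SAP 7.10.4.3.

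**2. What a patient with a stoma scores under the stated rule.**

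| How the form is answered | Items 1 to 5 | Total | Result |
|---|---|---|---|
| *Never* to 1, 2, 4, 5; any answer to 3 | 0, 0, {0, 2, 4 or 5}, 0, 0 | 0-5 | No LARS |
| As above, item 3 blank | four zeros, imputed 0 | 0 | No LARS |
| About the bag: frequent emptying, again within the hour | 0, 0, 4, 11, 0 | 15 | No LARS |
| As above, with gas and leakage | 7, 3, 4, 11, 0 | 25 | Minor |
| As above, with urgency | 7, 3, 4, 11, 16 | 41 | Major |
| Two items or fewer answered | - | - | Missing |

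The same clinical state can thus be missing or fall in any band.

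**3. Illustrative size.** Let *s* be the share of scored patients with a stoma, all taken to score 'No LARS', and *p* the 'No LARS' proportion in patients without a stoma. The pooled proportion is p(1 - s) + s, so its excess over *p* is s(1 - p).

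Inputs:
- TME share: 35% to 50%, from 1 - 0.65 and 1 - 0.50, the design rates in Protocol 13.3.
- Stoma among TME patients: 25%. This is the only figure in the documents (Protocol 2.0). It is a non-sphincter-sparing rate from stage II/III trials.
- p: 30% to 50%. This is an assumption; the documents give no value.

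Pooled:
- s = 0.35 x 0.25 = 0.0875, or 0.50 x 0.25 = 0.125.
- Lowest excess: 0.0875 x 0.50 = 0.044. Highest: 0.125 x 0.70 = 0.0875. That is about 4 to 9 points.

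TME patients only, a split the SAP does not plan:
- s = 0.25. The excess is 0.25 x 0.50 = 0.125 to 0.25 x 0.70 = 0.175, about 12 to 18 points.

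If the stoma share among TME patients is varied from 10% to 50%:
- Pooled: 0.35 x 0.10 x 0.50 = 0.018 to 0.50 x 0.50 x 0.70 = 0.175, about 2 to 18 points.
- TME only: 0.10 x 0.50 = 0.05 to 0.50 x 0.70 = 0.35, or 5 to 35 points.

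**The case against.** **Use after TME is deliberate.** The Protocol Background says LARS and FIQL were developed for follow-up after standard rectal surgery. That supports collecting LARS once bowel continuity is restored. It does not give the items a meaning while stool is diverted.

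**The direction is not fixed by the SAP.** A reader might infer that every patient with a stoma is scored 'No LARS'. The documents do not say so. The form gives these patients no instruction, and step 2 shows that a bag-based answer can reach any band and a mostly blank form is missing. This stands: overstatement of 'No LARS' is probable, not certain.

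**No split by surgery is planned.** A reader might infer that the plan will flatter function specifically after failed organ preservation. Tables 49 to 52 pool all QoL-evaluable patients, so that comparison arises only if someone makes it. This stands.

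**The inputs are soft.** The 25% comes from stage II/III disease, whereas this trial enrols cT1-3abN0 tumours judged suitable for local excision. It also leaves out temporary ostomies. The TME share ignores patients sent directly to TME and, in the other direction, those who decline it, for whom Table 27 has a row. The figures are illustrations only.

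**Stoma frequency is not hidden.** Stoma status is scored under CR29 and summarised in Tables 49 and 50. That is true, but a mean stoma score does not correct the LARS bands.

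**The unlisted fourth group might be a stoma category.** Nothing in SAP 7.10.4.3 or Table 52 says so.

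**Conclusion.** The gap is real and no other section closes it. The pooled LARS means, change scores and severity proportions can include scores that have no interpretation, and 'No LARS' is probably overstated. Under the assumptions in step 3, the excess is about 4 to 9 points pooled. It would be about 12 to 18 points among TME patients if results were split.

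Four stronger readings are not supported.
- Five stoma patients among 50 (10 points), or among 20 TME patients (25 points), is their gross contribution to the band. It is an upper bound on the excess, reached only if p = 0.
- The distortion cannot be said to be greatest at month 6, because the documents give no timing for stoma reversal.
- FIQL is not wholly inapplicable with a stoma. Leakage from a bag is possible, and its Depression/Self-Perception scale includes general health (Q1) and mood (Q4).
- Common scoring of the two versions of CR29 items 49-54 cannot be called an error here, since the SAP defers to the EORTC scoring manual, which is not among the documents.

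The outputs affected are secondary and descriptive. The primary endpoint and the two-stage decision are untouched. The change should still be made, because the rule as written can put patients without anorectal function in the best category.

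**What to change.** - **SAP 7.10.1.3:** when CR29 item 48 is yes at a visit, set LARS to 'not applicable - stoma', with no score and no imputation.
- **SAP 7.10.4.1:** restrict LARS means and change scores (Tables 49 and 50) to visits without a stoma.
- **SAP 7.10.4.3 and Table 52:** add a 'stoma present' row with all responders as the denominator, so that the rows sum to 100%. The proportion among patients without a stoma can be recovered from the same rows. Reconcile the four-group wording with the three bands listed.
- **FIQL (SAP 7.10.1.4 and 7.10.4.1):** keep the instrument, but show stoma visits separately for the leakage-based scales.

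The cost is SAP wording, one table row and slightly fewer LARS scores. No new data are needed, since item 48 is in the same booklet at every QoL visit.

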Appendix 1: Tables and Figures

Table 1. Patient Disposition

Data set: All Accrued Patients	
Accrued	Number of patients (%) N=** ** (**)
Treated	** (**)
On study	** (**)
Off study ⁽¹⁾	** (**)
Never Treated	** (**)

(1) Off all study therapy

Table 2: Follow-up of Patients

Data set: All Accrued Patients	
Number of patients alive	Number of patients (%) N=** *** (%)
Fellow-up (months)	
median	**
Minimum-maximum	**_**

Table 3: Accrual by Center

Data set: All Accrued Patients	
Center #1	Number of patients (%) N=** ** (**)
Center #2	** (**)
Center #3	** (**)
...	** (**)

Figure 1: Accrual by Calendar Time

[figure not shown]

Table 4: Eligibility and Reasons for Ineligibility and Major Protocol Violations

Data set: All Accrued Patients	
	Number of Patients (%) N=**
Eligible	** (**)
Not Eligible	** (**)
Reason for ineligibility	
<Reason 1>	**
<Reason 2>	**
...	**
Major protocol violation	
<violation type 1>	**
<violation type 2>	**
...	

Table 5: Pre-treatment Characteristics at Baseline

Data set: All Accrued Patients		Number of patients (%) N=**
Gender		
Female		** (**)
Male		** (**)
Age (years)		
N		**
Median		**
Min - Max		** - **
< 65		** (**)
≥ 65		** (**)
Race		
White		** (**)
Black or African American		** (**)
Native Hawaiian or Pacific Islander		** (**)
Asian		** (**)
Not reported (or refused)		** (**)
Unknown		** (**)
Height		
N		**
Median		**
Min-Max		** - **
Weight		
N		**
Median		**
Min-Max		** - **
BSA		
N		**
Median		**
Min-Max		** - **
ECOG Performance Status		
0		** (**)
1		** (**)
Months from First Histological Diagnosis to enrollment		
N		**
Median		**
Min - Max		** - **
Tumour Invasion based on pelvic MRI		
Submucosa		** (**)
Muscularis propria		** (**)
Muscularis propria no more than 5 mm into the subserosa/perirectal tissue		** (**)
Muscularis propria more than 5 mm into the subserosa/perirectal tissue		** (**)
Not visible on pelvic MRI		** (**)
cT-stage (based on pelvic MRI)		
T1		**(**)
T2		**(**)
T3a		**(**)
T3b		**(**)
Tumour Height from anal verge (cm)		
N		**
Median		**
Min - Max		** - **

Table 6: Baseline Pathology Results

Dataset :All Accrued Patients		Number of patients (%) N=**
Longest dimension of Invasive Carcinoma		
N		**
Median		**
Min – Max		** - **
Histology		
Adeno-carcinoma		** (**)
Squamous		** (**)
Other		** (**)
Histologic Grade		
Well -Differentiated		** (**)
Moderately Differentiated		** (**)
Not stated in report		** (**)
		** /**\
Deepest Layer of Invasion		
Mucosa		** (**)
Lamina Propria		** (**)
Muscularis mucosa		** (**)
Submucosa		** (**)
Muscularis propria		** (**)
Serosa		** (**)
Perirectal tissue		** (**)
Subserosa		** (**)
Depth of invasion into subserosa		
Median		**
Min-max		**.**
Not Stated in Report		** /**\
Deep Margin		
Positive for invasive carcinoma		**(**)
Median		**
Min-Max		**.**
Negative		**(**)
Not stated in Report		**(**)
Not Applicable		**(**)
Mucosal Margin		
Positive for invasive carcinoma		**(**)
Median		**
Min-Max		**.**
Negative		**(**)
Not stated in Report		**(**)
Not Applicable		**.**\
Pathologic T Stage		
T0		** (**)
T1		** (**)
T2		** (**)
T3		** (**)
Unknown		** (**)
Tumour deposits		
Yes		**(**)
No		**(**)

Table 7: Baseline Sigmoidoscopy/Colonoscopy and Other Radiology Investigations

Data set: All Accrued Patients	
	Number of Patients (%) N=**
Sigmoidoscopy	
Normal	** (**)
Abnormal, Non-malignant	** (**)
Abnormal, malignant	** (**)
Colonoscopy	
Normal	** (**)
Abnormal, Non-malignant	** (**)
Abnormal, malignant	** (**)
Other Radiology 1	
Result 1	** (**)
...	** (**)
...	

Table 8: Baseline Hematology

Data set: All Accrued Patients	
	Number of Patients (%) N=**
Hemoglobin	
Grade 0	** (**)
Grade 1	** (**)
Grade 2	** (**)
Grade 3	** (**)
Grade 4	** (**)
Not reported ⁽¹⁾	** (**)
WBC	
Grade 0	** (**)
Grade 1	** (**)
Grade 2	** (**)
Grade 3	** (**)
Grade 4	** (**)
Not reported ⁽¹⁾	** (**)
Absolute neutrophil count (ANC)	
Grade 0	** (**)
Grade 1	** (**)
Grade 2	** (**)
Grade 3	** (**)
Grade 4	** (**)
Not reported ⁽¹⁾	** (**)
Platelet	
Grade 0	** (**)
Grade 1	** (**)
Grade 2	** (**)
Grade 3	** (**)
Grade 4	** (**)
Not reported ⁽¹⁾	** (**)
Lymphocytes	
Grade 0	** (**)
Grade 1	** (**)
Grade 2	** (**)
Grade 3	** (**)
Grade 4	** (**)
Not reported ⁽¹⁾	** (**)
Basophils	
Normal	** (**)
>1-1.5xULN	** (**)
>1.5-2.0xULN	** (**)
>2.0-5.0xULN	** (**)
>5.0xULN	** (**)
Not reported ⁽¹⁾	** (**)
Monocytes	
Normal	** (**)
>1-1.5xULN	** (**)
>1.5-2.0xULN	** (**)
>2.0-5.0xULN	** (**)
>5.0xULN	** (**)
Not reported ⁽¹⁾	** (**)

Eosinophils	
Normal	** (**)
>1-1.5xULN	** (**)
>1.5-2.0xULN	** (**)
>2.0-5.0xULN	** (**)
>5.0xULN	** (**)
Not reported ⁽¹⁾	** (**)

Table 9: Baseline Biochemistry

Data set: All Accrued Patients	
	Number of Patients (%)
	Total N=**
Serum Creatinine	
Grade 0	** (**)
Grade 1	** (**)
Grade 2	** (**)
Grade 3	** (**)
Grade 4	** (**)
Not reported ⁽¹⁾	** (**)
Total bilirubin	
Grade 0	** (**)
Grade 1	** (**)
Grade 2	** (**)
Grade 3	** (**)
Grade 4	** (**)
Not reported ⁽¹⁾	** (**)
ALT	
Grade 0	** (**)
Grade 1	** (**)
Grade 2	** (**)
Grade 3	** (**)
Grade 4	** (**)
Not reported ⁽¹⁾	** (**)
Creatinine Clearance	
Grade 0	** (**)
Grade 1	** (**)
Grade 2	** (**)
Grade 3	** (**)
Grade 4	** (**)
Not reported ⁽¹⁾	** (**)

⁽¹⁾ Not done or outside the 30-day window prior to enrollment

Table 10: Baseline Coagulation

Data set: All Accrued Patients	
	Number of Patients (%)
	Total N=**
PT	
Grade 0	** (**)
Grade 1	** (**)
Grade 2	** (**)
Grade 3	** (**)
Grade 4	** (**)
Not reported ⁽¹⁾	** (**)
INR	
Grade 0	** (**)
Grade 1	** (**)
Grade 2	** (**)
Grade 3	** (**)
Grade 4	** (**)
Not reported ⁽¹⁾	** (**)
PTT	
Grade 0	** (**)
Grade 1	** (**)
Grade 2	** (**)
Grade 3	** (**)
Grade 4	** (**)
Not reported ⁽¹⁾	** (**)

⁽¹⁾ Not done or outside the 30-day window prior to enrollment

Table 11: Baseline Symptoms Status

Data set: All Accrued Patients						
	Number of patients (%) N=**					
	Worst grade	Any grade				
Patients with any symptom/finding at baseline	NR ** (**)	1 ** (**)	2 ** (**)	3 ** (**)	4 ** (**)	** (**)
Patients with particular symptom/finding, within body system:						
Body System 1 ⁽¹⁾	**(**)	**(**)	**(**)	**(**)	**(**)	**(**)
Event 1	**(**)	**(**)	**(**)	**(**)	**(**)	**(**)
Event 2	**(**)	**(**)	**(**)	**(**)	**(**)	**(**)
Event 3	**(**)	**(**)	**(**)	**(**)	**(**)	**(**)
...	**(**)	**(**)	**(**)	**(**)	**(**)	**(**)
Body System 2 ⁽¹⁾						
Event 1	**(**)	**(**)	**(**)	**(**)	**(**)	**(**)
...	**(**)	**(**)	**(**)	**(**)	**(**)	**(**)
()	**(**)	**(**)	**(**)	**(**)	**(**)	**(**)

⁽¹⁾ Patients may have more than one event within a body system

Table 12: Prior Concomitant Medications (Baseline)

Data set: All Accrued Patients	
	Number of patients (%)
	N=**
Any prior concomitant medication ⁽¹⁾	
No	** (**)
Yes	** (**)
Drug Name 1	** (**)
Drug Name 2	** (**)
....	

Table 13: Past or Current Major Medical Problems

Data set: All Accrued Patients	
	Number of patients (%)
	N=**
Patients Reporting at least one past or current major medical problem at baseline	
Medical Problem ⁽¹⁾	** (**)
...	** (**)

(1) patients may report more than one medical problem reported

Table 14: Tobacco Smoking History at Baseline

Data set: All Accrued Patients		Number of patients (%) N=**
Ever smoked any tobacco product		
Yes		** (**)
No		** (**)
Unknown		** (**)
Currently smoking		
Yes		** (**)
No		** (**)
Current Average number of cigarettes per day		
N		**
Median		**
Min - Max		** - **
Years from quitting smoking to enrollment		
N		**
Median		**
Min - Max		** - **
Years from beginning smoking cigarettes to enrollment		
N		**
Median		**
Min - Max		** - **
Total number of years of smoking cigarettes		
N		**
Median		**
Min - Max		**
Average number of cigarettes smoked per day		
N		**
Median		**
Min - Max		**
Average pack years of cigarettes smoked		
N		**
Median		**
Min - Max		** - **

Table 15: Number of Patients by Cycle of Chemotherapy

		Data Set: All Chemotherapy Treated Patients	
		Number of Patients (%)	
		FOLFOX N=**	CAPOX N=**
Cycle	1	** (**)	** (**)
	2	** (**)	** (**)
	3	** (**)	** (**)
	...		

Table 16: Number of Cycles of Chemotherapy per Patient

Data Set: All Chemotherapy Treated Patients		
	FOLFOX	CAPOX
Number of Cycles:		
N	**	**
Median	*	*
Min – Max	* – *	* – *

Table 17: Total Duration of Chemotherapy

Data Set: All Chemotherapy Treated Patients		
	FOLFOX	CAPOX
Duration in weeks:		
N	**	**
Median	*	*
Min – Max	* – *	* – *

Table 18: Number of Patients with Modifications of Chemotherapy

Table 19: Cumulative Dose

Data Set: All Chemotherapy Treated Patients						
Cumulative dose per patient (<unit>)	FOLFOX				CAPOX	
	Oxaliplatin	Leucovarin	Bolos Fluorouracil	Continuous Fluorouracil	Oxaliplatin	Capecitabine
	***	***	***	***	***	***
	** (**)	** (**)	** (**)	** (**)	** (**)	** (**)
	**	**	**	**	**	**
	** - **	** - **	** - **	** - **	** - **	** - **

Table 20: Actual Dose Intensity

Data Set: All Chemotherapy Treated Patients						
Dose intensity	FOLFOX				CAPOX	
	Oxaliplatin	Leucovarin	Bolos Fluorouracil	Continuous Fluorouracil	Oxaliplatin	Capecitabine
	***	***	***	***	***	***
	** (**)	** (**)	** (**)	** (**)	** (**)	** (**)
	**	**	**	**	**	**
	** - **	** - **	** - **	** - **	** - **	** - **

Table 21: Relative Dose Intensity

Data Set: All Chemotherapy Treated Patients						
Relative Dose intensity	FOLFOX				CAPOX	
	Oxaliplatin	Leucovarin	Bolos Fluorouracil	Continuous Fluorouracil	Oxaliplatin	Capecitabine
	** (**)	** (**)	** (**)	** (**)	** (**)	** (**)
	** (**)	** (**)	** (**)	** (**)	** (**)	** (**)
	** (**)	** (**)	** (**)	** (**)	** (**)	** (**)
	** (**)	** (**)	** (**)	** (**)	** (**)	** (**)

Table 22: Off Neoadjuvant Chemotherapy Summary

Data set: All Chemotherapy Treated Patients		Number of patients (%) N=**
Patients off Chemotherapy		** (**)
Reason off protocol therapy		
Treatment Completed		**
Progressive Disease (objective)		**
Symptomatic Progression		**
Intercurrent Illness – adverse events unrelated to protocol treatment		**
Adverse events related to protocol therapy		**
Patient Refusal (not related to adverse event)		**
Death		**
Other Reason		**

Table 23: Pre-excision Characteristics and MRI results

Data set: All Chemotherapy Treated Patients		Number of patients (%) N=**
Weight		**
N		**
Median		**
Min-Max		** - **
BSA		
N		**
Median		**
Min-Max		** - **
ECOG Performance Status		
0		** (**)
1		** (**)
cT-stage (based on pelvic MRI)		
T0		**(**)
Tis		**(**)
T1		**(**)
T2		**(**)
T3a		**(**)
T3b		**(**)
T3c		**(**)
T3d		**(**)
T4a		**(**)
T4b		**(**)
Tx		**(**)
Node positive disease		
Yes		** (**)
No		** (**)
Clear circumferential radial margin (CRM)		
Yes		** (**)
No		** (**)
Progressive disease		
Yes		** (**)
No		** (**)

Table 24: Pre-excision Sigmoidoscopy/Colonoscopy and Other Radiology Investigations

Data set: All Chemotherapy Treated Patients		Number of Patients (%) N=**
Sigmoidoscopy		
Normal		** (**)
Abnormal, Non-malignant		** (**)
Abnormal, malignant		** (**)
Colonoscopy		
Normal		** (**)
Abnormal, Non-malignant		** (**)
Abnormal, malignant		** (**)
Other Radiology Investigation 1		
Result 1		** (**)
...		** (**)
...		

Table 25: Pre-excision Extent of Disease

Data set: All Chemotherapy Treated Patients	
	Number of patients (%) N=**
Patients with disease assessment	** (**)
Patients with disease progression	** (**)
Number of Disease sites	
1	** (**)
2	** (**)
3	** (**)
4	** (**)
≥5	** (**)
Longest Diameter in mm	
<2	** (**)
2-5	** (**)
> 5-10	** (**)
> 10	** (**)
Site of Disease ⁽¹⁾	
Abdomen	** (**)
Adrenals	** (**)
Bone	** (**)
Brain	** (**)
Liver	** (**)
Lung	** (**)
Nodes	** (**)
Subcutaneous Tissue	** (**)
....	** (**)
Patients with new lesions	** (**)
Number of new lesions	
1	** (**)
2	** (**)
3	** (**)
4	** (**)
≥5	** (**)
Site of Disease ⁽¹⁾	
Abdomen	** (**)
Adrenals	** (**)
Bone	** (**)
Brain	** (**)
Liver	** (**)
Lung	** (**)
Nodes	** (**)
Pleura	** (**)
Skin	** (**)
Subcutaneous Tissue	** (**)
....	** (**)

Table 26: Plan of surgical Treatment

Data set: All Chemotherapy Treated Patients		Number of Patients (%) N=**
TAMIS/TEMS		** (**)
Mesorectal Excision (TME)		** (**)
No Surgery Planned (Patient Refusal)		** (**)
No Surgery Planned (Tumour excision not appropriate)		** (**)
Other		** (**)

Table 27: Surgery Summary

Data set: All Chemotherapy Treated Patients		Number of patients (%) N=**
Patients received tumour excision		** (**)
Procedure Performed		
TEMIS		** (**)
TAMIS		** (**)
TME		** (**)
Other		** (**)
Time in operating room (minutes)		
Median		**
Min-max		** --
Resection margins		
R0		** (**)
R1		** (**)
R2		** (**)
Mesorectal excision		
Total/complete		** (**)
Incomplete		** (**)
Unknown		** (**)
Subsequent Surgery Recommended		
Not applicable (TME performed)		** (**)
Yes		** (**)
Yes, but declined by patient		** (**)
No, complete tumour resection and ypT0 or ypT1good		** (**)
Other		** (**)
Patients with definitive decision not to have tumour excision		** (**)
Reason for definitive decision not to have tumour excision		
Intercurrent Illness		** (**)
Progressive Disease		** (**)
Patient Refusal		** (**)
Death		** (**)
Other		** (**)

Table 28: Pathology Results After Surgical Treatment

Dataset: All Chemotherapy and Excision/Surgery Treated Patients

	Number of patients (%) N=**
Site of tumor	
Rectum	** (**)
Nodes	** (**)
Other	** (**)
Longest dimension of Invasive Carcinoma	
N	**
Median	**
Min – Max	** – **
Lymphatic invasion	
Yes	** (**)
No	** (**)
Not stated in the report	** (**)
Vascular invasion	
Yes	** (**)
No	** (**)
Not stated in the report	** (**)
Histology	
Adeno-carcinoma	** (**)
Squamous	** (**)
Other	** (**)
Histologic Grade	
Well -differentiated	** (**)
Moderately differentiated	** (**)
Poorly differentiated	** (**)
Undifferentiated, anaplastic	** (**)
Grade cannot be assessed	** (**)
Not stated in report	** (**)
Deepest Layer of Invasion	
Mucosa	** (**)
Lamina Propria	** (**)
Muscularis mucosa	** (**)
Submucosa	** (**)
Muscularis propria	** (**)
Serosa	** (**)
Perirectal tissue	** (**)
Subserosa	** (**)
Depth of invasion into subserosa	
Median	**
Min-max	** – **
Not Stated in Report	

Deep Margin	
Positive for invasive carcinoma	**(**)
Median	**
Min-Max	**_**
Negative	**(**)
Not stated in Report	**(**)
Not Applicable	**(**)
Mucosal Margin	**(**)
Positive for invasive carcinoma	**(**)
Median	**
Min-Max	**_**
Negative	**(**)
Not stated in Report	**(**)
Not Applicable	**(**)
Pathologic T Stage	**(**)
T0	** (**)
T1	** (**)
T2	** (**)
T3	** (**)
Unknown	** (**)
Number of Nodes examined	
N	**
Median	**
Min-Max	** - **
Number of nodes with tumour	
N	**
Median	**
Min-Max	** - **
Tumour deposits	
Yes	**(**)
No	**(**)

Table 29: Radiotherapy Treatment

Data set: All Chemotherapy & Excision Treated Patients	
	Number of patients (%) N=**
Number of Patients with Radiation treatment	** (**)
Site of Radiotherapy	
Rectum	** (**)
Sigmoid colon	** (**)
Anus	** (**)
Duration of Radiotherapy	
Median	**
Min-max	** - **
Total Dose of radiation (cGy)	
Median	**
Min-max	** - **

Table 30: Summary of Organ Preservation

Dataset: All Accrued Patients		Number of Patients (%) N=**
Patients received neoadjuvant chemotherapy		
No		**(**)
Yes		**(**)
Disease Progression or no response		
Yes		**(**)
Disease Progression		**(**)
No Response based on Pre-excision MRI		**(**)
cT3ab stage		**(**)
node positive disease		** (**)
not clear circumferential radial margin (CRM)		** (**)
No response based on excision specimen		** (**)
node positive disease		**(**)
ypT2		**(**)
ypT1 tumours with:		
- poorly differentiated histology		**(**)
- lymphovascular invasion		**(**)
- positive margin within <1mm		** (**)
Treated with TME		** (**)
No		
Treated with TEMS/TAMIS		** (**)
Ypstage T0/T1 goodN0		
No		** (**)
Subsequent TME		** (**)
Yes		** (**)
Organ Preservation Rate (%) (95% CI)		
Over All Chemotherapy and Excision Treated Patients		** (**-**)
Over All Chemotherapy Treated Patients		** (**-**)

Table 31: Summary of Disease Outcomes

Data set: All Chemotherapy & Excision Treated Patients	Number of Patients (%)
	N=**
Patients who had Disease free survival (DFS) event	** (**)
Locoregional Relapse	**(**)
Site of Disease	
Rectum	**(**)
Pelvis	**(**)
Pelvic Lymph nodes	**(**)
Other	**(**)
Distant Disease	**(**)
Site of Disease	
Lung	**(**)
Liver	**(**)
Brain	**(**)
Distant lymph nodes	**(**)
Skin	**(**)
Ascites	**(**)
Pleural effusion	**(**)
Adrenal glands	**(**)
other	**(**)
Non-protocol therapy without documentation of site of failure	** (**)
Radiotherapy	**(**)
Chemotherapy	**(**)
Biologic therapy	
Death (due to any other reason)	**(**)
Patients who were censored	**(**)
Reason Censored	
Alive at the clinical cut-off	**(**)
Lost to follow-up	**(**)
3 year locoregional relapse rate (%) (95% CI)	**(**-**)
3 year distant relapse rate (%) (95% CI)	**(**-**)
3 year Disease free survival rate (%) (95% CI)	**(**-**)

Figure 2: Kaplan-Meier Curve for Locoregional Relapse Free Survival

Figure 3: Kaplan-Meier Curve for Distant Relapse Free Survival

Figure 4: Kaplan-Meier Curve for Disease Free Survival

Note: Same table and figures will be made for all chemotherapy treated patients.

Table 32: Acute Non-Hematologic Adverse Events

Data set: All Chemotherapy Treated Patients							
	NR	Number of patients (%) N=**					Any grade
		1	2	3	4	5	
Patients with any AE	** (**)	** (**)	** (**)	** (**)	** (**)	** (**)	** (**)
Patients with AE within category							
Category 1 ⁽¹⁾	**(**)	**(**)	**(**)	**(**)	**(**)	**(**)	**(**)
Event 1	**(**)	**(**)	**(**)	**(**)	**(**)	**(**)	**(**)
